Data file, identifier_patient_display_id_full	Descriptive	Variable name	Variable label, NEW prefix added to all labels "Implantation analyzer data, [specification ... to ...]: "	Variable level	Nominal values
implantation_analyzer_data	Yes	imp_ana_lv_amp_01	Sensing amplitude [mV]	scale	n.a.

The above analyses are performed for all 7 vector permutations, respectively:

- 01 LV1 tip to LV2 ring
- 02 LV1 tip to ICD
- 03 LV2 ring to LV3 ring
- 04 LV2 ring to ICD
- 05 LV3 ring to LV4 ring
- 06 LV3 ring to ICD
- 07 LV4 ring to ICD

Implantation Analyzer Data / LV / 7 Sensing Vectors / Not-measured

Data file, identifier_patient_display_id_full	Descriptive	Variable name	Variable label	Variable level	Nominal values
implantation_analyzer_data	No	imp_ana_lv_svect_no	-	nominal	No intrinsic rhythm Amplitude visible but too low to measure During intrinsic rhythm no R-wave visible Not done
data_SAR	Yes	imp_ana_lv_svect_no_SAR ³³	Implantation analyzer data: Any LV pacing vector	nominal	Amplitude visible but too low to measure During intrinsic rhythm no R-wave visible At least one vector measured

³² IF imp_ana_rv_thresh_no = No capture ... THEN imp_ana_rv_thresh_no_SAR = imp_ana_rv_thresh_no
ELSE IF imp_ana_rv_thresh ≠ missing THEN imp_ana_rv_thresh_no_SAR = Measured

³³ IF imp_ana_lv_svect_no = Amplitude visible but too low to measure
THEN imp_ana_lv_svect_SAR = Amplitude visible but too low to measure
ELSE IF imp_ana_lv_amp_0j_no = During intrinsic rhythm no R-wave visible
THEN imp_ana_lv_svect_no = During intrinsic rhythm no R-wave visible
ELSE IF any j=1-7 imp_ana_lv_amp_0j ≠ missing
THEN imp_ana_lv_svect_SAR = At least one vector measured

Implantation Analyzer Data / LV / 12 Pacing Vectors

Data file, identifier_patient_display_id_full	Descriptive	Variable name	Variable label, NEW prefix added to all labels "Implantation analyzer data, [specification ... to ...]: "	Variable level	Nominal values
implantation_analyzer_data	Yes	imp_ana_lv_imp_01	Pacing impedance [Ω]	scale	n.a.
implantation_analyzer_data	No	imp_ana_lv_thresh_01	Pacing threshold [V]	scale	n.a.
implantation_analyzer_data	No	imp_ana_lv_pulse_01	at Pulse width [ms]	scale	n.a.
data_SAR	Yes	imp_ana_lv_thresh_01_04 ³⁴	Pacing threshold [V] at 0.4 ms	scale	n.a.
data_SAR	Yes	imp_ana_lv_thresh_01_05 ³⁵	Pacing threshold [V] at 0.5 ms	scale	n.a.
implantation_analyzer_data	No	imp_ana_lv_pns_amp_01	at pacing amplitude [V]	scale	n.a.

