The above analyses are performed for all 7 vector permutations, respectively:

- 01 LV1 tip to LV2 ring
- 02 LV1 tip to ICD
- 03 LV2 ring to LV3 ring
- 04 LV2 ring to ICD
- 05 LV3 ring to LV4 ring
- 06 LV3 ring to ICD
- 07 LV4 ring to ICD

Implantation Device Data / LV / 7 Sensing Vectors / Not-measured

Data file, identifier_patient_display_id_full	Descriptive	Variable name	Variable label	Variable level	Nominal values
implantation_device_data	No	imp_lv_svect_no	-	nominal	No intrinsic rhythm Amplitude visible but too low to measure During intrinsic rhythm no R-wave visible Not done
data_SAR	Yes	imp_lv_svect_SAR ⁴⁶	Implantation device data, any LV pacing vector: Sensing amplitude	nominal	Amplitude visible but too low to measure During intrinsic rhythm no R-wave visible At least one vector measured

⁴⁶ IF imp_lv_amp_no = Amplitude visible but too low to measure
 THEN imp_lv_svect_SAR = Amplitude visible but too low to measure
 ELSE IF imp_lv_amp_no = During intrinsic rhythm no R-wave visible
 THEN imp_lv_svect_SAR = During intrinsic rhythm no R-wave visible
 ELSE IF any j=1-7 imp_lv_amp_0j ≠ missing
 THEN imp_lv_svect_SAR = At least one vector measured

Implantation Device Data / LV / Programmed Pacing Vectors

Final programmed pacing vectors are handled in the multipole_pacing CRFs.

Data file, identifier_patient_display_id_full	Descriptive	Variable name	Variable label, NEW prefix added to all labels "Implantation device data, first LV pacing vector: "	Variable level	Nominal values
implantation_device_data	Yes	imp_lv_first_imp	Pacing impedance [Ω]	scale	n.a.
implantation_device_data	No	imp_lv_first_thresh	Pacing threshold [V]	scale	n.a.
implantation_device_data	No	imp_lv_first_pulse	at Pulse width [ms]	scale	n.a.
data_SAR	Yes	imp_lv_first_thresh_04 ⁴⁷	Pacing threshold [V] at Pulse width 0.4 ms	scale	n.a.

Data file, identifier_patient_display_id_full	Descriptive	Variable name	Variable label, NEW prefix added to all labels "Implantation device data, second LV pacing vector: "	Variable level	Nominal values
implantation_device_data	Yes	imp_lv_sec_imp	Pacing impedance [Ω]	scale	n.a.
implantation_device_data	No	imp_lv_sec_thresh	Pacing threshold [V]	scale	n.a.
implantation_device_data	No	imp_lv_sec_pulse	at Pulse width [ms]	scale	n.a.
data_SAR	Yes	imp_lv_sec_thresh_04 ⁴⁸	Pacing threshold [V] at Pulse width 0.4 ms	scale	n.a.

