18.6. Hypotheses & Statistical Tests

There are no pre-defined statistical hypotheses.

⁸⁰ IF CMBLFL = Yes AND any CMCLAS = ACE inhibitors

⁸¹ IF CMBLFL = Yes AND any CMCLAS = Angiotensin receptor ...

⁸² IF CMBLFL = Yes AND any CMCLAS = Aldosterone blocker

⁸³ IF CMBLFL = Yes AND any CMCLAS = Betablocker ...

⁸⁴ IF CMBLFL = Yes AND any CMCLAS = Calcium channel blocker

⁸⁵ IF CMBLFL = Yes AND any CMCLAS = Digoxin

⁸⁶ IF CMBLFL = Yes AND any CMCLAS = Statins

⁸⁷ IF CMBLFL = Yes AND any CMCLAS = Diuretics

⁸⁸ IF CMBLFL = Yes AND any CMCLAS = Anticoagulation

⁸⁹ IF CMBLFL = Yes AND any CMCLAS = Antiplatelets

⁹⁰ IF CMBLFL = Yes AND any CMCLAS = Antiarrhythmics

⁹¹ IF CMBLFL = Yes AND any CMCLAS = ACE inhibitors OR
any CMCLAS = Angiotensin receptor ...

THEN med01_SAR= Yes ELSE med01_SAR = No

THEN med02_SAR= Yes ELSE med02_SAR = No

THEN med03_SAR= Yes ELSE med03_SAR = No

THEN med04_SAR= Yes ELSE med04_SAR = No

THEN med05_SAR= Yes ELSE med05_SAR = No

THEN med06_SAR= Yes ELSE med06_SAR = No

THEN med07_SAR= Yes ELSE med07_SAR = No

THEN med08_SAR= Yes ELSE med08_SAR = No

THEN med09_SAR= Yes ELSE med09_SAR = No

THEN med10_SAR= Yes ELSE med10_SAR = No

THEN med11_SAR= Yes ELSE med11_SAR = No

THEN med01_01_SAR= Yes
ELSE med01_02_SAR = No

19. Implantation Data: Plexa

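### Three SAP derivation rules (footnotes 33, 46 and 91) use variable names that contradict their own tables; followed literally, they give wrong descriptive tables for LV sensing and Plexa baseline medication

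*SAP*

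**What the plan says.** SAP 10.2 gives, for each block of LV sensing vectors, a raw field recording why sensing was not measured and a derived field that is reported. The raw fields are marked No in the Descriptive column, so these categories reach the report only through the derived variables.

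- **Footnote 33, analyzer data.** The table declares the source "imp_ana_lv_svect_no" and the reported variable "imp_ana_lv_svect_no_SAR". The first branch reads the declared source, then: "THEN imp_ana_lv_svect_SAR = Amplitude visible but too low to measure". The second branch is "ELSE IF imp_ana_lv_amp_0j_no = During intrinsic rhythm no R-wave visible", followed by "THEN imp_ana_lv_svect_no = During intrinsic rhythm no R-wave visible". The third assigns the measured category to `imp_ana_lv_svect_SAR`.
- **Footnote 46, device data.** The table declares the source "imp_lv_svect_no" and the reported variable `imp_lv_svect_SAR`. The rule starts "IF imp_lv_amp_no = Amplitude visible but too low to measure"; the second branch tests the same field, `imp_lv_amp_no`. All three branches write the declared reported variable. SAP 11.2 reuses this block at pre-hospital discharge (PHD) with the prefix `phd_`.
- **Footnote 91, Plexa baseline medication (SAP section 18).** The table reports `med01_02_SAR` as the combined ACE inhibitor or ARB row. The rule's positive branch is "THEN med01_01_SAR= Yes"; its negative branch sets `med01_02_SAR` to No.

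SAP 5.1 bases relative frequencies on non-missing data.

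**The concern.** SAP section 1 presents the document as the detailed instruction for all mandatory descriptive and inferential analyses, so these footnotes are the specification a programmer works from. Parallel rules show the intended logic. Footnotes 30 and 42 (RV, analyzer and device) and footnote 67 (LV at 3 months) read and write consistent names and keep both failure categories. Footnote 22 is the Ilivia counterpart of footnote 91 and assigns Yes to the correct variable. The differences in 33, 46 and 91 therefore look like slips and not choices.

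For footnote 46 the error runs one way. A patient whose LV signal was too low, or showed no R-wave, becomes missing and leaves the denominator, or is counted as measured if any of the seven vectors has an amplitude. LV sensing then looks better than the recorded data, in a study whose stated purpose (CIP 7.1) is to find residual device risks.

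**Working it through.** The plan states no figure here to reproduce. The check is to run each rule as written on every source category, treating a field that the SAP does not list as missing, and then to run the rule with the names corrected.

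**Footnotes 33 and 46**

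| Raw status, any amplitude recorded | Fn 33, declared variable | Fn 33, name used in the footnote | Fn 46 | Corrected rule |
|---|---|---|---|---|
| Too low, none | missing | too low | missing | too low |
| No R-wave, none | missing | missing | missing | no R-wave |
| No flag, at least one | missing | measured | measured | measured |
| No R-wave, at least one | missing | measured | measured | no R-wave |
| No intrinsic rhythm, none | missing | missing | missing | missing |
| Not done, none | missing | missing | missing | missing |

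For footnote 33:
- Under the declared name nothing is ever assigned, because two branches drop `_no` from the output name and the third writes to the raw field.
- If the footnote's own output name is accepted, the too-low and measured categories survive and the no-R-wave category is lost.
- Repairing only the condition in the second branch does not recover it, because the result still goes to the raw field, which is not reported.

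For footnote 46, only one category is reachable on the listed fields. Among non-missing patients the measured category is therefore 100%, whatever was recorded. PHD inherits this.

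**Footnote 91**

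With this rule alone, a user of an ACE inhibitor or ARB gets `med01_01_SAR` = Yes and `med01_02_SAR` missing, and a non-user gets `med01_02_SAR` = No. Yes is unreachable in the reported row.

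SAP section 1 describes one merged file, `data_SAR`, to which footnote 22 also writes. Two further cases follow:
- If footnote 22 has already run on all patients, its Yes is not overwritten and the combined row is right.
- If footnote 22 has run only on the Ilivia set (SAP 9.1), patients in both groups keep their Yes, but users in group B alone stay missing. With a users in both groups, b users in group B only, and n non-users, the table gives a/(a + n) where the true share is (a + b)/(a + b + n). The first is smaller whenever b and n are both above zero.

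**Missing brackets, footnotes 22 and 91**

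The condition has the form baseline AND ACE inhibitor OR ARB. With AND evaluated before OR, this is (baseline AND ACE inhibitor) OR ARB, so an ARB record that is not baseline would qualify. The text above both medication tables limits reporting to baseline medication, so the intended scope is clear and only the formula is loose.

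**The case against.** The strongest reply is that these are typing slips in shorthand. The intended output categories stand in the tables beside the footnotes, the SAP 5.1 layouts report missing counts, and amplitudes are tabulated for all seven vectors, so a programmer would probably notice. An entirely unfilled variable under footnote 33 would be obvious. That is fair and supports a low severity. It does not make the rules right, and the footnote 46 result is less conspicuous, because it yields a plausible table.

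A second reply is that `imp_lv_amp_no` may exist in the database export, since the 3-month form has the analogous `fu3_lv_amp_no`. The documents do not show the export, so the conclusion on footnote 46 is limited to the listed fields. The same reply does not rescue footnote 33: even if its unlisted field existed, the result would still go to the raw field.

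Several stronger readings are tempting and not supported:
- A reader might infer that footnotes 33 and 46 both read and write the wrong variables throughout. Footnote 46 writes the correct output variable, and footnote 33's too-low branch reads the correct source.
- A reader might infer that the Plexa baseline table cannot show ACE inhibitor or ARB use. The two classes have their own rows with consistent rules (footnotes 80 and 81); only the combined row is touched, and footnote 22 may already have filled it for some or all patients.
- A reader might infer that device safety conclusions are at risk. The affected sections state that no hypotheses are pre-defined, CIP 4.7.2 says LV sensing is not used for tachycardia diagnosis, and adverse events and device deficiencies are collected separately.

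**Conclusion.** The point holds as a specification error with minor consequences. As written:
- Footnote 33 can never report the no-R-wave category and never fills its declared variable.
- Footnote 46 can assign only the measured category at implantation and PHD, provided `imp_lv_amp_no` is not a real field.
- Footnote 91 alone cannot code the combined medication row as Yes.

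The damage is limited to LV sensing status at implantation and PHD and to one row of the Plexa baseline table. The 3-month LV sensing rule is sound and is reused at 6 months. No primary or secondary endpoint, test, analysis set or sample size is involved. The number of patients misreported cannot be estimated, because the documents give no count of LV sensing failures or of medication users.

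**What to change.** - **Footnote 33:** test `imp_ana_lv_svect_no` in both failure branches and write `imp_ana_lv_svect_no_SAR` in all three branches.
- **Footnote 46:** test `imp_lv_svect_no` in both failure branches (`phd_lv_svect_no` at PHD); leave the output variable as it is.
- **Footnote 91:** assign Yes to `med01_02_SAR`.
- **Footnotes 22 and 91:** write the condition as CMBLFL = Yes AND (ACE inhibitors OR ARB).

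The cost is a corrected set of SAP footnotes, with no new data and no change to any confirmatory analysis. A check of all derived names against their tables would be sensible at the same time, since similar slips occur elsewhere: footnote 53 fills the second-vector threshold result from the first-vector field, and footnote 61 writes to the raw variable and not to its derived version.

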- Exclusion of particular information from the evaluation of the above endpoint(s) in addition to the exclusion of patients from the analysis set.
- Descriptive analyses including tables and figures
- Statistical alternative hypothesis/hypotheses (HA) to analyze the above endpoint(s).
- Statistical tests intended to analyze the above hypothesis/hypotheses.

All variables are defined in tables using the following columns:

Data file	Name of a data file exported from the CDMS with one data row per unique identifier (e.g. patient specific "patient_display_ID_full"). Additionally, a new data file ("data_SAR") is generated by merging all relevant data from the original CDMS data files and generating derived variables (e.g. BMI from weight and height or date of first AE episode)				
Descriptive	Information whether data has to be presented with descriptive methods as defined in the following sub-chapter ("Yes") or data needed for generating of derived variables only ("No")				
Variable name	Original name of a variable in the CDMS data file or name of a derived variables (indicated with a suffix "_SAR");				
Variable label	Variable label which might be shortened ("...") if remaining clear; note that original labels from the CDMS data will be used for generating the Statistical Analysis Report unless a new label is defined in this document ("NEW")				
Variable level	Nominal, ordinal, scale (metric, continuous), or date				
Nominal values	Values might be shortened ("...") if remaining clear; note that original values from CDMS data will be used for generating the Statistical Analysis Report unless new nominal values are defined in this document ("NEW"); for numeric data this information is not applicable (n.a.)				

Data file, unique identifier	Descriptive	Variable name	Variable label	Variable level	Nominal values
patient_display_id_full					

2. Objectives

CIP chapter 7.1 Objectives

This study is designed as post market clinical follow-up study to identify and evaluate residual risks associated with the use of the Ilivia ICD family and the Plexa ICD lead that are unveiled or remained even after risk analysis, risk mitigation and successful conformity assessment. Furthermore, the study aims at providing additional data, as required by regulatory authorities.

3. Investigational Device

CIP chapter 4.7. Definition of the investigational Devices

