implantation_device_data	No	imp_lv_sec_imp_no	-	nominal	Out of range >3000 Out of range <200 Not measurable: no overpacing possible Not done
data_SAR	Yes	imp_lv_sec_imp_no_SAR ⁵²	Implantation device data, second LV pacing vector: Pacing impedance	nominal	Out of range Measured
implantation_device_data	No	imp_lv_sec_thresh_no	-	nominal	No capture with 7.5V possible Not measurable: no overpacing possible Not done
data_SAR	Yes	imp_lv_sec_thresh_no_SAR ⁵³	Implantation device data, second LV pacing vector: Pacing threshold	nominal	No capture with 7.5V possible Measured

⁵⁰ IF imp_lv_first_imp_no = Out of range >3000 OR
imp_lv_first_imp_no = Out of range <200 THEN imp_lv_first_imp_no_SAR = Out of range
ELSE IF imp_lv_first_imp ≠ missing THEN imp_lv_first_imp_no_SAR = Measured

⁵¹ IF imp_lv_first_thresh_no = No capture ... THEN imp_lv_first_thresh_no_SAR = imp_lv_first_thresh_no
ELSE IF imp_lv_first_thresh ≠ missing THEN imp_lv_first_thresh_no_SAR = Measured

⁵² IF imp_lv_sec_imp_no = Out of range >3000 OR
imp_lv_sec_imp_no = Out of range <200 THEN imp_lv_sec_imp_no_SAR = Out of range
ELSE IF imp_lv_sec_imp ≠ missing THEN imp_lv_sec_imp_no_SAR = Measured

⁵³ IF imp_lv_sec_thresh_no = No capture ... THEN imp_lv_sec_thresh_no_SAR = imp_lv_first_thresh_no
ELSE IF imp_lv_sec_thresh ≠ missing THEN imp_lv_sec_thresh_no_SAR = Measured

Implantation Device Data / LV / Programmed Delay

Data file, identifier_patient_display_id_full	Descriptive	Variable name	Variable label, NEW prefix added to all labels "Implantation device data: "	Variable level	Nominal values
implantation_device_data	No	imp_order_rvlv	Pacing order	nominal	RV first LV first
implantation_device_data	Yes, for the above groups "RV first" and "LV first"	imp_lvlv_delay	LV-LV delay [ms]	scale	n.a.
implantation_device_data	Yes, for the above groups "RV first" and "LV first"	imp_rvlv_delay	RV-LV delay [ms]	scale	n.a.

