11.2. Variables

PHD / General data

Data file, identifier patient_display_id_full	Descriptive	Variable name	Variable label, NEW prefix added to all labels "PHD data:"	Variable level	Nominal values
phd_general_data	No	phd_visdate	Date of follow-up	date	n.a.
phd_general_data	Yes	phd_not_done	visit not performed	nominal	True / False

The following variables are analyzed as defined for the Ilivia analysis set, as described in chapter 10.2 device data.

PHD Device Data / RA

PHD Device Data / RA / Not-measured

PHD Device Data / RV

PHD Device Data / RV / Not-measured

PHD Device Data / LV / 7 Sensing Vectors

PHD Device Data / LV / 7 Sensing Vectors / Not-measured

PHD Device Data / LV / Programmed Pacing Vectors

PHD Device Data / LV / Programmed Pacing Vectors / Not-measured

Note: all variable names have the prefix "phd_" instead of "imp_".

For the programmed first and second LV pacing vector here the pacing threshold should have been measured at pulse width 0.4 ms (phd_lv_first_thresh_04 and phd_lv_sec_thresh_04, "Pacing threshold [V] at Pulse width 0.4 ms").

As threshold measurements at other pulse durations than 0.4 will be discarded (see 10.2), the variables "Pacing threshold [V]" (phd_lv_first_thresh and phd_lv_sec_thresh) and "at Pulse width [ms]" (phd_lv_first_pulse and phd_lv_sec_pulse) are not needed for analysis.

However, phd_lv_first_thresh_no and phd_lv_sec_thresh_no have the additional option "Not measured at 0.4 ms".

⁵⁴ analysis_set_Ilivia_SAR = Yes

PHD / Device Data / LV / Vector Change

Data file, identifier patient_display_id_full	Descriptive	Variable name	Variable label, NEW prefix added to all labels "PHD data: "	Variable level	Nominal values
phd_device_data	Yes	phd_lv_change	Has any of the LV vectors been changed since implant	nominal	No Yes, first LV vector Yes, second LV vector Yes, both vectors
phd_device_data	Yes	phd_lv_change_reason	Primary reason for change	nominal	Phrenic nerve stimulation High LV pacing threshold PNS and high threshold better safety margin [...] CRT optimization [...] Other
phd_device_data	Reporting for each patient if the above variable = other	phd_lv_change_reason_co	[NEW] PHD data: Comments related to Primary reason for change	text	...
phd_device_data	Yes	phd_lv_change_pns	Phrenic nerve stimulation or high pacing threshold could successfully be resolved	nominal	Yes / No

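### SAP footnote 53 fills the second LV vector's no-capture status from the first vector's field, so a second-vector capture failure is tabulated correctly only when both vectors fail

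*SAP*

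**What the plan says.** SAP 10.2 tabulates, for each programmed LV pacing vector, whether a pacing threshold was obtained at implantation. The raw second-vector field, `imp_lv_sec_thresh_no`, has these codes: "No capture with 7.5V possible Not measurable: no overpacing possible Not done". It is marked as not descriptive, which under the column definitions in SAP section 1 means that it only feeds derived variables. What is tabulated is `imp_lv_sec_thresh_no_SAR`, with two listed values: no capture at 7.5 V, or measured.

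Footnote 53 gives the derivation in two branches:

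- where `imp_lv_sec_thresh_no` is coded as no capture: "THEN imp_lv_sec_thresh_no_SAR = imp_lv_first_thresh_no"
- "ELSE IF imp_lv_sec_thresh ≠ missing THEN imp_lv_sec_thresh_no_SAR = Measured"

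For the first vector, footnote 51 tests and assigns the same field: "IF imp_lv_first_thresh_no = No capture ... THEN imp_lv_first_thresh_no_SAR = imp_lv_first_thresh_no".

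SAP 11.2 applies the 10.2 definitions at pre-hospital discharge, including the block "PHD Device Data / LV / Programmed Pacing Vectors / Not-measured". SAP 13.2 (3 months) refers back to 11.2, and SAP 14.2 (6 months) refers back to 13.2. None of these sections restates or corrects the rule.

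**The concern.** The condition in footnote 53 concerns one vector and the assigned value comes from the other. The neighbouring rules do not cross vectors. Footnote 52, for second-vector impedance, stays with the second vector: "imp_lv_sec_imp_no = Out of range <200 THEN imp_lv_sec_imp_no_SAR = Out of range". Footnote 53 looks like an incomplete copy of footnote 51.

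It is nevertheless the stated derivation of a reported variable, and a programmer who follows it gets a wrong count. MultiPole Pacing is mandatory for group A CRT-D patients (protocol 8.5.6), and the second LV vector is what separates it from conventional CRT pacing. Within the programmed-vector block, this derived variable is the only tabulated no-capture result for that vector.

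**Working it through.** The SAP gives no figure to reproduce here, so the check is to apply the rule literally.

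**Inputs**

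- The rule: SAP 10.2, footnote 53, both branches.
- First-vector codes (`imp_lv_first_thresh_no`, SAP 10.2): no capture, not measurable, not done. There is no code for a measured threshold, so I infer that the field is empty when the first vector captured.
- Denominator: relative frequencies use non-missing data (SAP 5.1).
- Planned CRT-D patients in group A: 53 (protocol 8.8.1), used for illustration only.

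**Step 1: all status combinations.** Each vector can be measured, without capture, not measurable or not done, which gives 4 × 4 = 16 combinations. In the 12 where the second vector is not coded as no capture, footnote 53 and the corrected rule agree. The other 4 are:

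| First vector | Second vector | Footnote 53 returns | Corrected rule returns |
|---|---|---|---|
| Measured | No capture | missing | No capture |
| No capture | No capture | No capture | No capture |
| Not measurable | No capture | Not measurable (unlisted value) | No capture |
| Not done | No capture | Not done (unlisted value) | No capture |

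So 1 of the 4 is right. In the first row the second branch cannot rescue the patient: the first condition was true, so the branch that assigns measured is never reached.

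**Step 2: later visits.** At pre-hospital discharge, SAP 11.2 adds a further code to both vectors' fields, for thresholds not measured at 0.4 ms. If the first vector carries that code, the copied rule imports it too, which is one more unlisted result.

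**Step 3: illustration.** Assume 53 CRT-D patients, all with first-vector capture, of whom k have no capture on the second vector and the rest have a measured threshold. As written, the table shows 0/(53 − k), with k missing. Corrected, it shows k/53.

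| k | As written | Corrected |
|---|---|---|
| 1 | 0/52 = 0.0%, 1 missing | 1/53 = 1.9% |
| 3 | 0/50 = 0.0%, 3 missing | 3/53 = 5.7% |
| 5 | 0/48 = 0.0%, 5 missing | 5/53 = 9.4% |

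If 1 of 3 such patients also failed on the first vector, the table as written would show 1/51 = 2.0%, with 2 missing, instead of 3/53 = 5.7%.

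**The case against.** The best reply is that this is a one-token slip with an obvious intent. The derived variable lists only two values and the adjacent footnotes stay within one vector, so a careful programmer would probably put it right. Whether it reached the program cannot be told from the documents. That lowers the stakes but does not make the written rule correct.

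A reader might infer that second-vector failures vanish from the report altogether. The documents do not support that:

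- The 12-vector table at MultiPole Pacing programming (SAP 12.2, footnote 60) takes each vector's no-capture status from that vector's own field. SAP 10.2 also refers the final programmed vectors to those forms.
- SAP 13.2 tabulates adequacy of LV pacing at 3 months, with non-capture as a possible reason, though not split by vector.
- SAP 12.2 flags patients with no second vector programmed at pre-hospital discharge, 3 months and 6 months, and lists them with comments.
- SAP 11.2 tabulates vector changes and their reasons, including a high LV threshold, and this is reused at later visits.
- The standard tables in SAP 5.1 show missing counts, so a patient whose derived value is blank still appears there, though without the reason.

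A reader might also take the 9% in protocol Table 8e as the expected size, about 5 of 53 patients. That figure describes patients with too few capturing LV vectors. It is not a rate of lost capture on a vector already programmed as second. All 12 vectors must be measured before programming, and thresholds below 2.5 V are recommended (protocol 8.5.6). A patient short of capturing vectors may therefore have no second vector programmed at all, which the unaffected flags would show.

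**Conclusion.** The error stands as written: footnote 53 gives the right code for a second-vector capture failure only when the first vector also fails. Its reach is the second-vector threshold-status table at implantation, pre-hospital discharge, 3 months and 6 months. The results there are descriptive, and no hypothesis, sample size, or primary or secondary endpoint depends on them, so this is a minor correction.

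The blank result in the commonest pattern, where the first vector captures, rests on the inference that its field is empty when a threshold was obtained. The documents give no rate for the event, so the understatement of 1.9 to 9.4 percentage points for 1 to 5 failures is an illustration under the stated assumptions and not a forecast. It would not be sound to conclude that the study's reporting on MultiPole Pacing as a whole is compromised.

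**What to change.** In SAP 10.2, change the first branch of footnote 53 to `THEN imp_lv_sec_thresh_no_SAR = imp_lv_sec_thresh_no`. Apply the same correction to the `phd_`, `fu3_` and `fu6_` derivations, and check the analysis program for the same slip. The cost is one token in the SAP plus the matching program lines; no data collection, design element or endpoint changes.
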